## 7.6 Domain-Specific Derivations

### 7.6.1 Adverse Events

Refer to the BHV3000 Core SAP for exposure-adjusted multiple occurrences of unique AEs.

Exposure-adjusted multiple occurrences of unique AE calculations will be based on the following reference dates according to safety analysis period:

- On-DBT: reference start date is DBT start date, reference end date is DBT end date, and reference last date is earlier of (1) DBT last date + 7 days and (2) OL rimegepant start date – 1 day.
- On-OL rimegepant: reference start date is OL rimegepant start date, reference end date is OL rimegepant end date, and reference last date is OL rimegepant last date + 7 days.
- On-DB or OL rimegepant: reference start date is DB or OL rimegepant start date, reference end date is DB or OL rimegepant end date, and reference last date is DB or OL rimegepant last date + 7 days.
- On-treatment: reference start date is the study drug start date, reference end date is study drug end date, and reference last date is study drug last date + 7 days.

### 7.6.2 eDiary

#### 7.6.2.1 eDiary Reference Time Point Date and Epoch

##### Reference Time Point Date Derivation

Reference time point date/time and epoch will only be derived for records with non-missing standard format character result/finding values.

- Evening report headache log
  - Select headache-related characteristics and non-study medication parameters with the same finding date/time: The reference time point date/time will be set to the headache start date/time, if not missing.
    - Parameters will include the following: headache (yes, no); headache start date/time; aura only event (yes, no); headache last at least 30 minutes (yes, no); severity (none, mild, moderate, severe); unilateral (yes, no); pulsate (yes, no); worsen or avoid physical activity (yes, no); nausea (yes, no); vomiting (yes, no); photophobia (yes,

- no); phonophobia (yes, no); aura (yes, no); triptan (yes, no); ergotamine (yes, no); other medication (yes, no).
  - Headache end date/time and headache end (ended, still continuing) parameters with the same finding date/time: The reference time point date/time will be set to headache end date/time, if the headache end date/time is not missing.
  - Study medication for headache or aura parameters with the same finding date/time: The reference time point date/time will be set to the study medication for headache or aura date/time, if not missing.
    - Parameters will include the following: study medication for headache or aura (yes, no); study medication for headache or aura date/time; number of tablets taken; confirm number of tablets taken (yes, no).
  - Additional study medication for headache or aura parameters with the same finding date/time: The reference time point date/time will be set to additional study medication for headache date/time, if not missing.
    - Parameters will include the following: additional study medication for headache (yes, no); additional study medication for headache or aura date/time; number of additional tablets taken; confirm number of additional tablets taken (yes, no).
  - Follow-up headache log
    - Headache end date/time and headache continuing (yes, no) parameters with the same finding date/time: The reference time point date/time will be set to headache end date/time, if not missing.
    - Non-study medication triptan and ergotamine parameters: The reference time point date/time will be set to the last non-missing headache start date/time from evening report headache logs with finding date/time  $\leq 24$  hours at or before the follow-up headache log finding date/time.
    - Study medication for headache parameters with the same finding date/time: The reference time point date/time will be set to the study medication for headache or aura date/time, if not missing.
      - Parameters will include the following: study medication for headache or aura (yes, no); study medication for headache or aura date/time; number of tablets taken; confirm number of tablets taken (yes, no).
  - Scheduled dosing report parameters with the same finding date/time: The reference time point date/time will be set to the study medication date/time, if not missing.
-

- Parameters will include the following: took study medication today (yes, no); study medication date/time; number of tablets taken; confirm number of tablets taken (yes, no).
- Medication reconciliation form date missed and number of tablets taken parameters with the same finding date/time: The reference time point date/time will be set to the date missed, if not missing. Note that time will be missing.

Otherwise, the reference time point date/time will be set to the eDiary finding date/time.

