3.4 Definition of Migraine Days

A Migraine Day is defined as any calendar day which the subject experiences a qualified migraine headache (onset, continuation or recurrence of the migraine headache). A qualified migraine headache is defined as a migraine with or without aura, lasting for ≥ 30 minutes, and meeting at least one of the following criteria (A and/or B):

A) ≥ 2 of the following pain features:

- Unilateral location,
- Pulsating quality (throbbing),
- Moderate or Severe pain intensity,
- Aggravation by or causing avoidance of routine physical activity (e.g. walking or climbing stairs)

B) ≥ 1 of the following associated symptoms:

- Nausea and/or Vomiting,
- Photophobia and phonophobia

During the double-blind, treatment phase, if the subject takes a migraine-specific medication (i.e. triptan or ergotamine) during aura or to treat a headache on a calendar day, then it will be counted as a migraine day regardless of the duration and pain features/associated symptoms. The use of study medication on non-scheduled dosing days is only permitted during the open-label, extension phase. **Dosing with study medication on non-scheduled dosing days is not permitted during the double-blind, treatment phase.**

A moderate to severe migraine day is a migraine day with a migraine reported with moderate or severe pain intensity.

For the full definition of Migraine Days, please refer to Section 15.3 Appendix 3.

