5.2 Inclusion Criteria

1. Signed Written Informed Consent

- a) Written informed consent must be obtained from the subject in accordance with requirements of the study center's institutional review board (IRB) or ethics committee, prior to the initiation of any protocol-required procedures.
- b) Subjects must be able to read.

2. Target Population

Subject has at least 1 year history of migraine (with or without aura) consistent with a diagnosis according to the International Classification of Headache Disorders, 3rd Edition², including the following:

- a) Age of onset of migraines prior to 50 years of age
 - b) Migraine attacks, on average, lasting 4 - 72 hours if untreated
 - c) Per subject report, 4-18 migraine attacks of moderate or severe intensity per month within the last 3 months prior to the Screening Visit (month is defined as 4 weeks for the purpose of this protocol)
 - d) 6 or more migraine days during Observation Period
 - e) Not more than 18 *headache days* during the Observation Period
 - f) Ability to distinguish migraine attacks from tension/cluster headaches
 - g) Subjects on prophylactic migraine medication are permitted to remain on therapy if the dose has been stable for at least 3 months (12 weeks) prior to the Observation Period, and the dose is not expected to change during the course of the study.
 - i. Subjects may remain on one (1) medication with possible migraine-prophylactic effects, excluding CGRP antagonists [biologic or small-molecule], during the double-blind treatment phase.
-

-
- ii. Concomitant use of a CGRP antagonist, such as erenumab or fremanezumab, is prohibited.
 - iii. Subjects who previously discontinued prophylactic migraine medication must have done so at least 90 days prior to the Screening Visit.
- h) Subjects with contraindications for use of triptans may be included provided they meet all other study entry criteria
3. Age and Reproductive Status
- a) Male and female subjects ≥ 18 years
 - b) Women of childbearing potential (WOCBP) and non-sterile men must be using two acceptable methods of contraception to avoid pregnancy throughout the study in such a manner that the risk of pregnancy is minimized. See Section 5.6 for the definition of WOCBP. Males with vasectomy are considered surgically sterile provided the procedure occurred greater than 6 months (24 weeks) prior to study participation.

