    - Efficacy date: (1) Complete reference time point date from any question from the evening report headache log or follow-up headache log, or (2) non-missing OL rimegepant date on a non-scheduled day (see Sections [7.6.2.2](#) and [7.6.2.3](#)).
    - OP start date: Earliest reference time point date from the OP epoch.
    - OP end date: Latest reference time point date from the OP epoch.
  - Miscellaneous composite dates
-

- Last DBT visit date: Maximum of the following: (1) latest eDiary reference time point date < OL rimegepant start date; (2) latest complete visit date from Visit Date CRF records without “follow-up” in foldername and visit date < OL rimegepant start date. This will be used to assess eDiary compliance.
- Last OLE visit date: Maximum of the following: (1) latest eDiary reference time point date ≥ OL rimegepant start date; (2) latest complete visit date from Visit Date CRF records without “follow-up” in foldername and visit date ≥ OL rimegepant start date. This will be used to assess eDiary compliance.
- Last DB or OL rimegepant visit date: Maximum of last DBT visit date and last OLE visit date for subjects whose as-treated treatment group is rimegepant; last OLE visit date/time for subjects whose as-treated treatment group is placebo. This will be used to assess eDiary compliance.
- Last contact date: (1) Earliest complete death date from the AE CRF, if it exists; (2) otherwise, the maximum complete date of the following: AE start/stop; COVID-19 visit only for in-person or remote visits; ECG; eDiary reference time point; informed consent; IWRS randomization; laboratory collection; menstrual period start/stop; non-study medication start/stop; physical measurement; procedure; rating scale; questionnaire; study completion/discontinuation from Subject Status CRF (DBT, OLE, follow-up); vital sign; visit.
- COVID-19 visit date: (1) Complete record date, if it exists; otherwise, complete date the visit was planned to occur for a missed visit (see Section 9.1.1).
- Death date: Last contact date derived only for subjects who died (see Section 6.5.1.1).

No imputations are performed on these derived dates. Complete dates are those with valid, non-missing day, month, and year.

See Section 7.6.2.1 for the reference time point date/time and epoch derivations.

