  - b. “Yes” response to the question about taking triptan to treat headache or during aura #@ or question about taking ergotamine to treat headache or during aura #@, along with complete reference time point date/time#@, in the on-DBT efficacy or on-OL rimegepant efficacy analysis period.

Date/time parameters and questions marked with “#” are identified from the evening report headache log. Date/time parameters and questions marked with “@” are identified from the follow-up headache log.

Migraine dates are determined from complete reference date/times based on eDiary parameters above.

Only unique days of efficacy data are included in analyses. If there are multiple responses on the same day, then the most severe migraine will be chosen.

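### The SAP dates a headache's qualifying answers to its start and has no rule for continuation days, which the protocol counts as migraine days

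*SAP*

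**What the plan says.** Protocol 3.4, repeated in Appendix 3, defines a migraine day by calendar day, and the day qualifies through "onset, continuation or recurrence of the migraine headache". Protocol 5.2 admits people with "Migraine attacks, on average, lasting 4 - 72 hours if untreated", so attacks that cross midnight are to be expected.

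SAP 7.6.2.2 says that it applies the Appendix 3 criteria. The dates come from SAP 7.6.2.1:

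- **Evening report** (headache yes/no, severity, pain features, symptoms; triptan, ergotamine and other medication): "The reference time point date/time will be set to the headache start date/time, if not missing".
- **Headache end and end status:** "The reference time point date/time will be set to headache end date/time, if the headache end date/time is not missing". Without an end time they take the finding date.
- **Follow-up log, triptan and ergotamine:** "The reference time point date/time will be set to the last non-missing headache start date/time from evening report headache logs", within a 24-hour look-back.
- **Study medication:** the dose date.
- **Anything else,** including evening-report answers with no recorded start: the finding date.

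SAP 7.6.2.2 takes pain features and symptoms from the evening report only, and then states: "Migraine dates are determined from complete reference date/times based on eDiary parameters above". Each date is kept once. No sentence extends a headache over the dates between start and end.

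SAP 7.3 defines an efficacy date, which feeds the proration denominator, much more broadly: "Complete reference time point date from any question from the evening report headache log or follow-up headache log". SAP Section 8 reports no changes from the protocol's planned analyses.

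**The concern.** The protocol makes continuation sufficient for a migraine day. The SAP's dating rule collects the answers that establish a migraine on the start date and says nothing explicit about later dates. The same later dates can still become efficacy days through the end or still-continuing record. A day spent in migraine could then be divided by but not counted.

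The derivation feeds the primary endpoint, the 50% responder endpoint, and the Month 1 and whole-phase secondaries. The backward dating of triptan and ergotamine answers also touches the rescue-medication secondary. It affects the protocol rule that such use makes its own calendar day a migraine day as well. If continuation days drop out, an attack that becomes shorter without becoming rarer leaves the count unchanged. The measured quantity would then differ from the one for which the planned 1-day advantage was stated.

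**Working it through.** **1. The plan's own figure.** Inputs from Protocol 9.3 and SAP 5: 370 per group, difference 1 day, SD 3.75. Level 0.05 is from Protocol 9.6, taken as two-sided because 95% intervals are reported. SE = 3.75 × √(2/370) = 0.2757; 1/0.2757 = 3.627; power = Φ(3.627 − 1.960) = 95.2%. The stated figure of roughly 95% reproduces.

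**2. A worked case.** Onset is Monday 22:00, after that day's report. Tuesday's evening report records the true Monday start, qualifying features and a headache still continuing. The follow-up log gives the end as Wednesday 10:00.

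| Date | Protocol | SAP, strict | SAP, loose | Efficacy day |
|---|---|---|---|---|
| Mon | yes | yes (start) | yes | yes |
| Tue | yes | no | yes (still continuing, finding date) | yes |
| Wed | yes | no | yes (end date) | yes |
| Total | 3 | 1 | 3 | 3 |

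The strict reading takes migraine dates only from the records that carry the qualifying features. The loose reading takes them from every parameter listed in SAP 7.6.2.2, which includes the end time and the still-continuing status. If this were the only attack in a fully recorded month, the SAP 6.3.1.1 proration gives 28 × 3/28 = 3 days under the loose reading and 28 × 1/28 = 1 day under the strict one.

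**3. Possible scale on the strict reading.** Assume that onset is uniform over the day, each attack produces one record with its true start, and each attack lasts D hours. Mean calendar dates touched = 1 + D/24. Share on continuation dates only = (D/24)/(1 + D/24).

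| D | Dates touched | Uncounted share |
|---|---|---|
| 4 h | 1.17 | 0.167/1.167 = 14% |
| 12 h | 1.50 | 0.5/1.5 = 33% |
| 24 h | 2.00 | 1/2 = 50% |

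The eligibility range of 4 to 72 hours is for untreated attacks. Protocol 5.5 allows acute treatment, so attacks in the trial would tend to be shorter.

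**4. Consequence for power.** If a share f is lost equally in both arms, the counted difference is 1 − f days.

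| f | Difference | Power, SD scaled by 1 − f | Power, SD fixed at 3.75 |
|---|---|---|---|
| 0.143 | 0.857 | 95.2% | 87.5% |
| 0.333 | 0.667 | 95.2% | 67.7% |
| 0.50 | 0.50 | 95.2% | 44.2% |

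The documents give no frequency of continuation-only days, so none of these rows is an estimate for this trial.

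**The case against.** The strongest reply is that this is an ambiguity and not an established undercount, and much of that reply stands.

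- A reader might infer that every headache record is dated to the start. That is wrong: end records, study-medication records and records without a start are dated otherwise.
- A reader might infer that the trial counts attack onsets and not migraine days. The documents do not support this. Diary reports are daily. If a continuing headache is entered next evening with qualifying features and either a start on that day or no start, the day counts even on the strict reading. The documents do not show how the eDiary handles this. The loose reading also gives the protocol's count of 3 in the worked case.
- A reader might infer bias between arms or a loss of power. Neither is shown. The rule is the same in both arms and in the observation period, and if the SD shrinks with the count, power stays at 95.2%.
- A reader might treat the version 4.0 revision note about dropping two-day counting as proof of the strict reading. It describes superseded text and is not relied on here.
- Version 10.0 of the SAP was changed after final database lock, and SAP Section 4 places an unblinded analysis at Week 12. Replacing the primary derivation now would redefine the endpoint with results known.

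What the reply does not remove is the conflict between the texts. The protocol makes continuation sufficient, the SAP dates the qualifying answers to the start with no rule for later dates, and Section 8 says nothing has changed. A primary endpoint that can be computed as 1 or 3 from the same diary entries is not fully specified.

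**Conclusion.** The point holds as an undeclared conflict between the protocol's definition and the SAP's derivation of the primary endpoint. On the strict reading, a headache logged with its true start and closed in the follow-up log counts on its start date only, and its continuing and end dates can sit in the denominator as non-migraine days. The sentence on migraine dates in SAP 7.6.2.2 can also be read to count those dates.

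The size is unknown. The 14%, 33% and 50% figures rest on uniform onset, one record per attack with the true start, and fixed durations of 4, 12 and 24 hours. Days re-entered with a same-day start or no start reduce the loss. The supported consequence is uncertainty about which quantity is measured.

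**What to change.** In SAP 7.6.2.2, state that a qualified migraine headache counts on each calendar date from its start date to its end date, or to the last finding date at which it is still continuing. Make every such date an efficacy day as well, so that filled dates do not enter the numerator alone. Apply the rule identically in the OP, DBT and OLE.

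Two safeguards are needed:

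- Count a date as moderate or severe only where that intensity was reported for it. Carrying the log's severity forward belongs in a sensitivity analysis, because it could label mild days as moderate or severe in the first secondary endpoint.
- Test the dating of follow-up-log triptan and ergotamine answers both ways, headache start against finding date. Neither is always the dose date.

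Report the start-date count alongside. Where results are already unblinded, keep the existing derivation in place, add the protocol-definition count as a labelled sensitivity analysis, and declare the departure in Section 8.

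The cost is one derivation to reprogram and a stop rule for headaches with no recorded end. The start, end and continuing fields are already collected.

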### Epoch Derivation

Epoch is defined based on the date part of derived date/times, as follows:

- OP: Reference time point date before the DBT start date or DBT start date missing
- DBT: (1) Reference time point date on or after the DBT start date and before the OL rimegepant start date, or (2) reference time point date on or after the DBT start date, if OL rimegepant start date missing
- OLE: Reference time point date on or after the OL rimegepant start date.

#### 7.6.2.2 eDiary Migraine Days

For migraine day analyses, a day of efficacy data is defined as any non-missing eDiary efficacy date (see Section 7.3).

A migraine day is defined as a day of efficacy data with either (1) or (2):

- 1) Qualified migraine headache based on the following criteria per BHV3000-305 Protocol Appendix 3:
  - “Yes” response to the question about having a headache# with complete reference time point date/time#, or non-missing headache start date/time# (see Section 7.3)
  - Lasting for  $\geq 30$  minutes, defined as any of the following:
    - “Yes” response to the question about the headache lasting  $\geq 30$  minutes#
    - Headache end date/time# – headache start date/time#  $\geq 30$  minutes, where headache end date/time and headache start date/time have the same finding date/time
    - Finding date/time# – headache start date/time#  $\geq 30$  minutes and headache end status is still continuing#, where headache start date/time and headache end status have the same finding date/time
    - Headache end date/time@ – headache start date/time#  $\geq 30$  minutes, where headache end date/time is from the follow-up headache log with earliest finding date/time  $\leq 24$  hours on or after the finding date/time of a still continuing headache from the evening report headache log
  - Meeting at least one of the following criteria (a or b):

- a.  $\geq 2$  of the following pain features based on “yes” response to questions with the same finding date/time:
    - i. Unilateral location#,
    - ii. Pulsating quality (throbbing)#,
    - iii. Moderate or severe pain intensity#
    - iv. Aggravation by or causing avoidance of routine physical activity (e.g. walking or climbing stairs)#
  - b.  $\geq 1$  of the following associated symptoms based on “yes” response to questions with the same finding date/time:
    - i. Nausea#
    - ii. Vomiting#
    - iii. Both photophobia# and phonophobia#
- 2) No qualified migraine headache but meeting either of the following criteria:
- a. Non-missing date/time of (1) study drug to treat headache or during aura#@ during the on-DBT efficacy analysis period, or (2) OL rimegepant on a non-scheduled day during the on-OL rimegepant efficacy analysis period (see Sections 7.3 and 7.6.2.3).
  - b. “Yes” response to the question about taking triptan to treat headache or during aura #@ or question about taking ergotamine to treat headache or during aura #@, along with complete reference time point date/time#@, in the on-DBT efficacy or on-OL rimegepant efficacy analysis period.

Date/time parameters and questions marked with “#” are identified from the evening report headache log. Date/time parameters and questions marked with “@” are identified from the follow-up headache log.

Migraine dates are determined from complete reference date/times based on eDiary parameters above.

Only unique days of efficacy data are included in analyses. If there are multiple responses on the same day, then the most severe migraine will be chosen.

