15.3 Appendix 3 – Definition of Migraine Days

Migraine Day: Any calendar day in which the subject experiences a qualified migraine headache (onset, continuation, or recurrence of the migraine headache). A qualified migraine headache is defined as a migraine with or without aura, lasting for ≥ 30 minutes, and meeting at least one of the following criteria (a and/or b)

a) ≥ 2 of the following pain features:

- Unilateral location,
- Pulsating quality (throbbing),
- Moderate or severe pain intensity,
- Aggravation by or causing avoidance of routine physical activity (e.g. walking or climbing stairs)

b) ≥ 1 of the following associated symptoms:

- Nausea and/or vomiting
- Photophobia and phonophobia

If the subject took a migraine-specific medication (i.e., study medication [open-label, extension phase only], triptan or ergotamine) during aura or to treat headache on a calendar day, then it will be counted as a migraine day regardless of the duration and pain features/associated symptoms. The use of study medication on non-scheduled dosing days is only permitted during the open-label, extension phase; **dosing with study medication on non-scheduled dosing days is not permitted during the double-blind, treatment phase.**

A moderate to severe migraine day is a migraine day with a migraine reported with moderate or severe pain intensity.

Headache Day: Any calendar day in which the subject experiences a qualified headache (initial onset, continuation, or recurrence of the headache). A qualified headache is defined as:

- a qualified migraine headache (including an aura-only event that is treated with acute migraine-specific medication), or
 - a qualified non-migraine headache, which is a headache that lasts ≥ 30 minutes and is not a qualified migraine headache, or
 - a headache of any duration for which acute headache treatment is administered.
-

Acute Migraine-specific Medication Treatment Day: Any calendar day during which the subject took a migraine-specific medication (i.e., study medication [open-label, extension phase only], triptan or ergotamine). The use of study medication on non-scheduled dosing days is only permitted during the open-label, extension phase; **dosing with study medication on non-scheduled dosing days is not permitted during the double-blind, treatment phase.**

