### **7.3 Derived Dates**

Derived dates for defining analysis periods are defined as follows:

---

- eDiary reference time/point date/time: See Section 7.6.2.1.
  - eDiary dosing dates:
    - Study drug to treat headache or during aura date/time: Complete reference time point date/time from any of the following date/time questions: study medication to treat headache or during aura from the evening report headache log or follow-up headache log; additional study medication to treat headache or during aura from the evening report headache log.
    - Imputed OL rimegepant to treat headache date/time: Complete reference time point date/time from “yes” response to question about having already taken study medication to treat headache from the scheduled dosing report. Derived only if both of the following criteria are met:
      - Reference time point date/time on or after the IWRS Week 12 kit assigned local date/time
      - There are no complete reference time point dates on the same day as the “yes” response from any of the following questions: study medication to treat headache or during aura date/time from the evening report headache log or follow-up headache log; additional study medication to treat headache or during aura date/time from the evening report headache log; date of missed scheduled dosing report or evening report headache log from the medication reconciliation form; study medication date/time from the scheduled dosing report.
    - Study drug date/time: Study drug to treat headache or during aura date/time, imputed OL rimegepant to treat headache date/time, or complete reference time point date/time from any of the following questions: date of missed scheduled dosing report or evening report headache log from the medication reconciliation form (note that time is not collected); study medication date/time from the scheduled dosing report.
      - DBT: Reference time point date/time before the IWRS Week 12 kit assigned local date/time (reference time point date before the IWRS Week 12 kit assigned local date for medication reconciliation form data) or the IWRS Week 12 kit assigned local date/time missing
      - OL rimegepant: Reference time point date/time on or after the IWRS Week 12 kit assigned local date/time (reference time point date on or after the IWRS Week 12 kit assigned local date for medication reconciliation form data)
    - Study drug start date/time: Earliest study drug date/time.

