## 7.4 Analysis Periods

Analysis periods are defined as follows:

- eDiary efficacy endpoints (migraine days, rescue medication days), based on the date part of derived date/times
  - OP: Reference time point date in the OP epoch (see Section 7.6.2.1).
  - On-DBT efficacy: Reference time point date in the DBT epoch on or before the DBT last date + 1 day. This period is used to assess efficacy during the DBT phase.
  - Post-DBT pre-OL rimegepant efficacy: Reference time point date in the DBT epoch after the DBT last date + 1 day. This period is used only in eDiary efficacy listings.
  - On-OL rimegepant efficacy: Reference time point date in the OLE epoch on or before the OL rimegepant last date + 1 day. This period is used to assess efficacy during the OLE phase.

- Follow-up efficacy: Reference time point date in the OLE epoch after the OL rimegepant last date + 1 day. This period is used only in eDiary efficacy listings.
  - OR efficacy endpoints (MSQoL, MIDAS)
    - On-DBT efficacy: Measurement date after the DBT start date through the earlier of (1) DBT last date + 1 day and (2) OL rimegepant start date. This period is used to assess OR efficacy during the DBT phase for evaluable mITT subjects.
  - Pre-treatment characteristics and safety endpoints
    - Pre-treatment: Measurement date/time on or before the study drug start date/time. Note that AEs with imputed start date equal to the study drug start date are **not** part of this period (refer to the BHV3000 Core SAP for AE start date imputation). This period is used to derive baseline values and to assess pre-treatment safety endpoints.
    - Pre-rimegepant: Measurement date/time on or before the DB or OL rimegepant start date/time. Note that AEs with imputed start date equal to the DB or OL rimegepant start date are **not** part of this period. This period is used to derive rimegepant baseline values and to assess pre-rimegepant safety endpoints for DB or OL rimegepant treated subjects.
    - On-DBT safety: Measurement date/time after the DBT start date/time through the earlier of DBT last date + 7 days and OL rimegepant start date/time. Note that AEs with imputed start date equal to the DBT start date are part of this period, while AEs with imputed start date equal to the OL rimegepant start date are **not** part of this period. This period is used to assess safety endpoints on DBT.

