## 8 CHANGES TO PLANNED ANALYSES IN THE PROTOCOL

There are no changes to planned analyses in the protocol at this time.

---

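### SAP 7.6.2.2 lets a blinded tablet logged as headache treatment create a double-blind migraine day, which the protocol's definition does not allow

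*SAP*

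**What the plan says.** SAP 7.6.2.2 gives two routes to a migraine day. Criterion 1 is the qualifying migraine, for which it cites Protocol Appendix 3. Criterion 2 is a fallback, headed "No qualified migraine headache but meeting either of the following criteria". It has three parts:

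- 2a(1) is met by a recorded date and time of "study drug to treat headache or during aura#@ during the on-DBT efficacy analysis period".
- 2a(2) is met in the open-label phase by rimegepant taken on a day outside the every-other-day schedule.
- 2b is met by a triptan or ergotamine in either phase.

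SAP 7.3 builds the date used in 2a(1) from eDiary entries for "study medication to treat headache or during aura from the evening report headache log or follow-up headache log", plus additional tablets entered in the evening report log. It sets no open-label limit on that date. SAP 7.4 says of the on-DBT efficacy period: "This period is used to assess efficacy during the DBT phase".

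The protocol has the same kind of fallback but with a narrower list. For the double-blind phase, Section 3.4 applies it "if the subject takes a migraine-specific medication (i.e. triptan or ergotamine) during aura or to treat a headache on a calendar day". Appendix 3 gives the list as "study medication [open-label, extension phase only], triptan or ergotamine) during aura or to treat headache on a calendar day". SAP Section 8 states: "There are no changes to planned analyses in the protocol at this time".

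**The concern.** Two places in the protocol agree that study medication does not make a migraine day in the double-blind phase. The SAP says that it does, and names that phase explicitly. Anyone programming from the SAP would therefore classify some double-blind days against the protocol's definition of the outcome being counted.

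What is at stake is the derivation of the primary endpoint (Weeks 9 to 12), of the secondary endpoints for the whole double-blind phase and for the first month, and of the 50% responder endpoint when the non-qualifying headache was moderate or severe. A reader of the protocol would not know that these counts can include such days.

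**Working it through.** **1. The definitions side by side.** Take a double-blind day with a headache or aura that does not qualify as a migraine.

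| Recorded that day | Protocol 3.4 and Appendix 3 | SAP 7.6.2.2 |
|---|---|---|
| Triptan or ergotamine | Migraine day | Migraine day (2b) |
| Blinded tablet logged as headache or aura treatment, no triptan or ergotamine | Not a migraine day | Migraine day (2a(1)) |
| Neither | Not a migraine day | Not a migraine day |

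Only the middle row differs.

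**2. A literal record.** A subject has a mild, bilateral headache for 20 minutes, with no associated symptoms and no triptan, and enters the scheduled tablet in the evening headache log as treatment. The headache fails the 30-minute requirement and the feature requirement. The protocol does not count the day; the SAP does. If the same headache is recorded as moderate, the SAP also counts it as a moderate or severe day, so it enters the responder endpoint.

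**3. Comparison with the open-label clause.** 2a(2) counts an open-label tablet only on a non-scheduled day, so a scheduled tablet alone never makes a migraine day there. 2a(1) has no such limit. Off-schedule dosing is barred in the double-blind phase (Protocol 3.4), so in a compliant subject 2a(1) can fire only on a scheduled tablet, which is the kind that 2a(2) leaves out.

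**4. What the clause can do to the counts.** It applies only when criterion 1 is not met, so it never removes a day. It is confined to the on-DBT period, and no study drug exists in the Observation Period, so baseline is untouched. It applies to both blinded arms.

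**5. Shift in the treatment difference.** Let h be the non-qualifying headache or aura days per 28 days without a triptan or ergotamine, and p the chance that a scheduled tablet on such a day is logged as treatment. With tablets on about half of days, the added days in one arm are h × ½ × p. The change in the difference between arms is

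½ × (h_R × p_R − h_P × p_P),

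where R is rimegepant and P is placebo. The documents give neither h nor p. If both are equal across arms, the change is 0. If h differs by 1 day and p is common, it is 0.05 day at p = 0.1, 0.25 day at p = 0.5, and 0 at p = 0 (all assumed values). The sign follows whichever arm has the larger product.

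**6. Scale against the plan's power.** Inputs from Protocol 9.3 and 9.6: 370 per group, difference 1 day, SD 3.75, alpha 0.05. A two-sided test is assumed; SAP 6.3 states two-sided intervals.

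- Standard error = 3.75 × √(2/370) = 0.276.
- 1/0.276 = 3.627, and 3.627 − 1.960 = 1.667, so power is 95.2%. This reproduces the stated figure of roughly 95%.

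| Difference if the clause moved it (assumed) | Power |
|---|---|
| 0.8 day | 82.7% |
| 0.9 day | 90.4% |
| 1.0 day | 95.2% |
| 1.1 days | 97.9% |
| 1.2 days | 99.2% |

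These rows show sensitivity in both directions. They are not estimates of what the clause does.

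**The case against.** The strongest reply is that the clause may hardly ever fire. Subjects are told to dose on schedule whether or not they have a migraine, and to treat migraine with standard-of-care medication (Protocol 4.3.2). Scheduled doses have their own eDiary report (SAP 6.2.6.1). A day is affected only if the tablet is also, or instead, entered in a headache log as treatment and the day does not count for another reason. That stands as a limit on size. It does not remove the conflict. SAP 6.2.6.1 itself plans to tabulate double-blind tablets recorded in more than one subject-reported source and mentions erroneous eDiary use, so such records are foreseen.

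Three stronger readings are tempting, and the documents do not support them.

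- *The clause could cost up to the whole treatment effect.* With h = 2 to 4 and p = 0.1 to 0.5, the within-arm formula gives 2 × ½ × 0.1 = 0.1 to 4 × ½ × 0.5 = 1.0 added days. Those inputs are assumed, and days added within one arm are not a change in the difference between arms. Nor does 18 − 6 = 12 bound h: it comes from Observation Period entry limits, and untreated headaches shorter than 30 minutes are not headache days at all.
- *It dilutes the effect.* This requires active drug to turn migraines into lesser headaches that are then logged as treated with the tablet. If placebo subjects have more such headaches, or log the tablet this way more often, the difference widens.
- *It shaped the Week 12 result.* The revision history says criterion 2a was modified in version 10.0, after final database lock, for the Addendum Report. SAP Section 4 places the Week 12 analysis earlier. Item 2a already existed (version 6.0 amended it), but its wording at that time is not shown.

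**Conclusion.** The conflict is real and rests on the text alone: the SAP's double-blind migraine-day definition is wider than the protocol's, and the departure is undeclared. It can only add post-baseline migraine days, in both arms. The number of such days, and the size and direction of any effect on the treatment difference, cannot be determined from the documents; the effect may be negligible. Whether the clause was applied in the Week 12 analysis is also not shown. It still warrants correction, because it sits in the derivation of the primary endpoint and readers cannot tell which definition produced the result.

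**What to change.** Remove 2a(1) from SAP 7.6.2.2, so that in the on-DBT period only 2b can turn a non-qualifying day into a migraine day, as Protocol 3.4 and Appendix 3 provide.

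If the Week 12 analysis already used 2a(1), declare the departure in SAP Section 8 and report the primary and migraine-day secondary analyses under the protocol definition alongside the results as run. Reporting both avoids silently replacing a primary derivation after unblinding.

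In either case, state which wording of criterion 2a was used for the Week 12 analysis, and tabulate by arm the double-blind days that qualify only through 2a(1). That table would settle the size question.

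The cost is one clause, one table and a small re-run on existing data.
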